3.4.2 Secondary study parameters

Secondary parameters of this study are:

- gait biomechanics (assessed with 3D-gait analysis);
- diversity, intensity and enjoyment of participation (assessed with the Children's Assessment of Participation and Enjoyment (CAPE)).
- walking speed (assessed during the ECWT).

Gait biomechanics

Instrumented gait analysis will be used to determine the biomechanical effects of the AFO. Baseline (pre-intervention) measurements of gait biomechanics will be done while walking barefoot (BF), with shoes only and with the subject's current ('old') AFO-FC. Gait analysis while wearing AFO-FC will be included in the evaluation measurements of each AFO configuration and will be repeated in the long-term follow-up measurements of the subject's optimal AFO. To control for varying effects of different shoes, patients will be asked to wear the same shoes during follow-up measurements as they were wearing during baseline measurements. The subject will walk on a 10 meter walkway in the laboratory, which is equipped with a force platform and a 3D-motion analysis system (OptoTrak) (Northern Digital Instruments, Waterloo, Canada). This system tracks 3D position of markers, which are attached to the subject, thereby enabling computing 3D positions of body segments within time series. A total of three walking trials will be done for each condition (e.g. BF) and individual data on joint angles and net joint moments (via inverse dynamics) around the hip, knee and ankle will be calculated for each trial. Data will be averaged to compare biomechanical output between conditions (e.g. BF and shoes), different AFO configurations (e.g. $T1_{k1}$ and $T1_{K2}$), and measurement moments ($T0_{deliver}$, $T1_{K}$, and $T2_{Kopt}$). Also gait parameters, such as step length, step width and cadence, will be calculated. The averaged data of gait parameters will be related to differences in other study parameters, such as EC of walking and daily activity.

Diversity, intensity and enjoyment of participation

Participation will be measured with the Dutch version of Children's Assessment of Participation and Enjoyment (CAPE) (68-70), which is a valid (70;71) and reliable (68;70) instrument to measure participation in recreation and leisure activities for children with and without disabilities, aged between 6 and 21 years old. This self-assessment questionnaire contains 55 items, each concerning a specific activity. These activities are sub-divided into formal and informal domains and belong to a particular type of activity (recreational, active physical, social, skill-based, or self-improvement). CAPE measures in which activities the child participates (diversity), the frequency of the child's participation (intensity), with whom and where activities take place and the child's enjoyment of participation in activities. In this study only the dimensions diversity, intensity and enjoyment will be assessed. Overall scores will be calculated for each dimension and sub-scores will be calculated for different domains and types of activity.

Walking speed

As described in chapter 3.4.1, the subject's walking speed will be assessed during the ECWT.

3.4.3 Other study parameters

Other study parameters are:

- personal and family characteristics (assessed with the intake questionnaire and the Bronnen van Steun en Spanning (BSS));
- disease characteristics (assessed with a physical exam);
- functional walking ability (assessed with the Functional Assessment Questionnaire (FAQ));
- functional mobility (assessed with the Functional Mobility Scale (FMS));
- medical needs and treatment goals (assessed with the Goal Attainment Scaling (GAS));
- physical fitness (assessed with physical fitness testing);
- AFO properties (assessed with the BRUCE device);
- adherence (assessed with a motivation diary and the @monitor (83));
- Satisfaction

Personal and family characteristics

Personal and family characteristics will be determined by means of an intake questionnaire. Personal characteristics will include: date of birth, sex, weight, height, leg length, use of assistive devices, hours of organized sports per week, grade and kind of education. Family characteristics will include family structure, siblings, parental employment, social economic status, level of education, and cultural background. Additionally, sources of stress and support in parents will be assessed with a Dutch questionnaire 'Bronnen van Steun en Spanning' (BSS) (72).

Disease characteristics

A standard physical examination will be done to describe disease characteristics (e.g. type and location of CP), and determine primary motor disorders (e.g. spasticity), gross motor function (GMFCS (58)), gait pattern (classification of Rodda et al. (18)), and gait type (according to classification of Becher (73)).

Functional walking ability

The subject's functional walking ability will be determined with The Functional Assessment Questionnaire (FAQ), which is a valid and reliable parent-report instrument to determine

changes in functional walking ability in CP children (74). It contains ten descriptions of walking ability in daily life, varying form non-ambulatory to ambulatory, of which parents have to choose the one that best describes the child's typical walking ability with the use of any needed assistive devices.

Functional mobility

The subject's functional mobility will be assessed using the Functional Mobility Scale (FMS) (75), which is included in the physical exam. This scale classifies functional mobility by rating the child's usual walking ability at three specific distances (5, 50, and 500 meters), according to the need for assistive devices (e.g. crutches) or mobility aids, such as a wheelchair. The scale can be completed by therapist or parents and is demonstrated to be valid and reliable in children with CP and sensitive to detect change after surgical intervention (75).

Medical needs and treatment goals

The subject's treatment goals and medical needs will be assessed using Goal Attainment Scaling (GAS) (76). GAS is commonly used to assess individual progress in rehabilitation and is a responsive (77) and reliable (78) method in terms of measuring changes in activity and participation in children with CP.

Physical fitness

Physical fitness will be assessed by an aerobic and anaerobic exercise test on a bicycle ergometer. The test will be performed according to a recently developed protocol (VUmc, Amsterdam, the Netherlands), which is found to be feasible and reliable in children with CP (79;80). Subjects will start with measuring resting metabolism, followed by a warming-up of two minutes. After the warming-up, the maximal aerobic test will start by gradually increasing the load until maximum effort is reached. The subject's heart rate (HR), respiratory exchange ratio (RER), and rate of perceived exhaustion (RPE) will be continuously assessed during the test. Criteria, based on these parameters, are set to define the moment maximal effort is reached. Physical fitness will be defined as oxygen uptake at the moment maximal effort is reached and will be expressed as $VO2_{max}$ (ml⁻¹·kg⁻¹·min⁻¹). After a cool-down and period of rest (approximately twenty minutes), the anaerobic 20 seconds Wingate Anaerobic cycling Test (20s-WAnT) will be performed. During this test, subjects will pedal as fast as possible against a high constant resistance to determine anaerobic power (peak power and mean power). Anaerobic power can be used as outcome measure for functional capacity in children with CP (81).

AFO properties

Assuming spring-like behaviour of the AFO, stiffness and neutral ankle angle will be assessed with BRUCE (82), which is a recently developed device for measuring mechanical AFO properties.

Adherence

Subjects are asked to keep a motivation diary to note when he/she was (not) wearing his/her AFO during the day and, if applicable, the reason for taking it off. To objectively measure treatment adherence, the adherence-to-treat monitor (@monitor (83)) will be placed into the shaft of the intervention AFO. By measuring temperature differences over time, the @monitor registers whether the AFO is worn or not. The monitor will measure during the last 2 weeks of the follow-up period, simultaneously with the SAM.

Satisfaction

Degree of satisfaction with an AFO will be rated with a scale from 0-10, in which a rate of zero means 'not satisfied at all' and a rate of 10 represents 'complete satisfaction'.

3.5 Study procedures

3.5.1 Measurement schedule

Baseline measurements for this study will be scheduled simultaneously with regular consultancies to limit the total amount of visits to the medical center. According to the regular schedule, all subjects will come to the medical center every two weeks within the preintervention period, in which the new AFO will be manufactured.

Baseline measurements (visit I)

The first visit to the medical center will be at the moment of casting (TO_{cast}). After signing the informed consent by parents and/or child, a physical examination will be performed to determine the child's anthropometric data, disease characteristics, gait pattern, and GMFCS level. The FMS and FAQ will also be completed and medical needs and treatment goals will be described using GAS. During this visit, parents fill in the intake questionnaire to obtain information on relevant personal and environmental factors. After the physical examination, subjects will perform the ECWT. At the end of the TO_{cast} visit, subjects will receive a motivation diary, and they will be asked to keep this diary during the pre-intervention period.

Baseline measurements (visit II)

Two weeks later, when patients come to the medical center to fit the new AFO (TO_{fit}), the physical fitness test will be performed. The researcher will also determine properties (i.e. stiffness) of the subject's current AFO using the BRUCE device. At the end of the TO_{fit} visit, subjects will receive the SAM to measure daily activity during the week before the next visit is scheduled.

Baseline measurements (visit III)

At the moment of delivery of the new AFO (T0_{deliver}), child and parent(s) will rate the current AFO in terms of satisfaction. (One of the) parents and child are asked to complete the CAPE questionnaire one or two days prior to this visit and they will hand it in together with the SAM and motivation diary during the T0_{deliver} visit. During the visit, the properties of the first AFO configuration (either rigid, stiff or flexible) will be determined by the researcher using the BRUCE device. The new AFO-FC will be tuned according to the method of Owen (65). Then, 3D-gait analysis will be performed in three walking conditions: BF, shoes, the current ('old') AFO-FC (if applicable),. Subjects will wear the new AFO-FC the subsequent four to eight weeks and will receive a new motivation diary, which should be kept during this period (until the next visit).

Baseline measurements with intervention AFO (visit IV, V, and VI)

During the period that the AFO configuration is worn, subjects will also wear the SAM for one week. After wearing the first intervention AFO-FC, subjects will come to the medical center for the evaluation measurements (T1_K). During this visit, 3D-gait analysis and ECWT will be performed, and the FMS and FAQ will be completed. The researcher will ask both the child and parent(s) to rate the worn AFO in terms of satisfaction. Then, properties of the new AFO configuration will be determined and the second AFO-FC will be tuned. Only during visit IV (T1K1), a 3D-gait analysis with the new configuration (K2) will be performed directly,to measure the immediate biomechanical effects of the AFO. The subject will wear the second AFO-FC for four to eight weeks (acclimation period will be matched according to total time that the first AFO-FC is worn), after which the same evaluation measurements will be done (including SAM). The motivation diary will be kept until the next visit to the medical center. This time schedule and set of measurements will be repeated for the third AFO-FC.

Optimal AFO selection (visit VI)

When the short-term follow-up measurements for all AFO configurations are completed, data will be analyzed and the subject's most optimal AFO will be selected. Selection of the subject's optimal AFO will be based on data of gait analysis (primarily on the knee angle in midstance), ECWT, and degree of satisfaction of the child and parent(s). Subsequently, the

Neuro Swing[®] ankle joint system of the subject's AFO-FC will be configured according to what is considered as optimal.

Long-term follow-up measurements (visit VIII)

The subject will wear the optimal AFO-FC during a period of twelve to twenty weeks, to ensure full habitation before long-term follow-up measurements will be performed ($T2_{kopt}$). Measurements at $T2_{kopt}$ will include the CAPE and SAM (of which data will be assessed during the week prior to the visit), adherence (data with the @monitor (83) will be assessed two weeks prior to the visit), 3D-gait analysis, ECWT, FAQ, FMS, and GAS.

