The rigid configuration of the Neuro Swing[®] system will not allow any dorsal or plantar flexion during walking, while the stiff and flexible configuration of the Neuro Swing[®] system will. For stiff configuration, the ankle joint system will be equipped with the spring that best approaches the stiffness of the subject's baseline AFO. For the flexible configuration, the system will be equipped with a spring that is less stiff (if the spring of the stiff configuration is the "fifth" (strongest), the flexible AFO will be configured with the "fourth" spring of the Neuro Swing[®] package).

Tuning

To further ensure fair comparison of AFO efficacy of different configurations, tuning of AFO-footwear combination (AFO-FC) should be done adequately and similarly for each AFO configuration. Tuning involves modification of the alignment of the AFO-FC in order to optimize gait kinetics and kinematics (64). The position of lower limb segments is described relative to the force of gravity, which acts vertically. The angle of the segment relative to the vertical, referred to as shank to vertical angle (SVA), can be expressed in degrees of incline or recline from the vertical (65). Most efficient gait is assumed to be achieved with a optimal SVA in midstance, which should be 10-12° inclined. Owen (65) recently introduced a clinical algorithm for the design and tuning of AFO-FCs, aiming to achieve the most optimal SVA. By using this algorithm for each AFO prescription, it is assumed that tuning of each AFO-FC will be adequate and for each AFO configuration.

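### Visit III tunes the new AFO-footwear combination before recording the only baseline gait analysis, with no safeguard that the shoes-only and old-AFO trials use unmodified footwear

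*Protocol*

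**What the plan says.** Protocol 3.5.1 describes visit III (T0deliver) as a sequence. Satisfaction with the current AFO is rated, and the first new stiffness configuration is measured on the BRUCE device. Next, "The new AFO-FC will be tuned according to the method of" a cited publication. The following sentence reads "Then, 3D-gait analysis will be performed in three walking conditions: BF, shoes, the current ('old') AFO-FC", the last condition applying only to children who have a current AFO.

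Section 3.4.2 gives these recordings their status: "Baseline (pre-intervention) measurements of gait biomechanics will be done while walking barefoot (BF), with shoes only and with the subject's current ('old') AFO-FC". The same section sets a footwear rule: "patients will be asked to wear the same shoes during follow-up measurements as they were wearing during baseline measurements". Its stated purpose is to control for the effects of different shoes.

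Section 3.3 defines the procedure: "Tuning involves modification of the alignment of the AFO-FC in order to optimize gait kinetics and kinematics". It also says that the ankle joint used in the study has adjustable alignment.

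For the evaluation visits (IV to VI), section 3.5.1 places gait analysis and the Energy Cost of Walking Test of the worn configuration first, and only afterwards: "Then, properties of the new AFO configuration will be determined and the second AFO-FC will be tuned".

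**The concern.** A baseline labelled pre-intervention should be complete before any step of the intervention is carried out. Here the first intervention step, tuning the new device together with the footwear, comes before the baseline gait recording on the same day. What is tuned is a combination that includes the shoe, and the same shoe is meant to serve at baseline and follow-up. The protocol does not say that footwear changes are removed for the baseline trials, or that a separate pair is used.

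What is at stake is the reference condition for gait. Section 3.1.1 defines the baseline as measurement in shoes alone, with the current AFO as an addition where there is one. Gait biomechanics is a secondary outcome by section 3.4.2, but it is named in the primary objective and in research questions 1 and 1a. Under section 3.6.3, T0 values are compared with T1 and T2 in a linear mixed model, and changes in gait are related by regression to changes in walking efficiency and daily activity. A baseline recorded after tuning cannot be recovered later for that child.

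**Working it through.** No figure in the protocol bears on this point. Its one design calculation, the sample size in 3.2.4, concerns energy cost, whose baseline is taken at the casting visit. The check is therefore a comparison of the procedures as written.

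1. **Order within the visits.**

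| Visit | First | Afterwards |
|---|---|---|
| III (T0deliver) | New AFO-footwear combination tuned | Gait analysis barefoot, in shoes, in old AFO |
| IV to VI (T1) | Gait analysis and energy cost test of the worn configuration | Next configuration tuned |

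   Both passages mark the order with the word *then*, so the sequence is stated and not merely implied by the listing. At visit IV a further gait analysis follows tuning, but it is explicitly a measurement of the new configuration's immediate effect, not of the condition being left behind.

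2. **Is there an earlier baseline gait recording?** No. Table 2 ticks 3D gait analysis at T0deliver, T1 and T2 only. Section 3.4.2 names the same three moments, and the descriptions of visits I and II contain no gait analysis.

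3. **Does tuning alter the shoe?** The protocol leaves this open.
   - Pointing towards the shoe: the object tuned is the AFO-footwear combination. The study cited for the definition of tuning has wedges in its title. Section 3.3 keeps mechanical properties other than stiffness equal across configurations, although each configuration is tuned. BRUCE, which measures stiffness and neutral angle, is listed before tuning, which fits best if tuning leaves the orthosis itself unchanged.
   - Pointing away: section 3.3 says alignment can be adjusted in the ankle joint, and Appendix A treats neutral angle as part of the AFO configuration. The protocol's own text nowhere mentions a change to the shoe.

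4. **Which baseline data could be affected?**

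| Baseline measurement | When recorded | Exposed if the shoe is altered? |
|---|---|---|
| Energy cost (primary) | T0cast, visit I | No, precedes tuning |
| Step activity (primary) | Week before T0deliver | No, precedes tuning |
| Gait, barefoot | T0deliver, after tuning | No, no footwear worn |
| Gait, shoes only | T0deliver, after tuning | Yes |
| Gait, old AFO with footwear | T0deliver, after tuning | Yes |

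5. **Which analyses inherit the exposure?** Those that use change in gait from T0: the T0-T1-T2 comparison of gait measures and the regressions on gait change. The comparison among the three stiffness configurations (3.6.2) and the selection of the optimal AFO (3.5.1) rest on T1 data and are not exposed.

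6. **Size.** This cannot be calculated. The protocol gives no amount of tuning, no share of children whose shoes would be changed, and no standard deviation for any gait variable.

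**The case against.** The strongest reply is that altered footwear is an inference. Tuning may be done wholly in the ankle joint, and what the cited tuning sources prescribe cannot be checked from the protocol. In that case the order within the visit would have no consequence through the shoe. This stands, and it is why the point is conditional.

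A second reply is that even a modified shoe, worn in every condition, holds footwear constant and isolates the orthosis. That would be a legitimate contrast, but the protocol does not claim it; it calls the data pre-intervention. Nor is constancy assured, because each later configuration is tuned again, and a change made at visit III would belong to whichever stiffness was randomised first.

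A reader might infer more than the text supports, in three ways:
- That the child has already walked in the new AFO before baseline. Visit III does not say so, and it describes the wearing period as following the visit.
- That part of the treatment effect is lost from the pre-post contrast. The protocol gives nothing from which to derive the effect of an altered shoe on gait in shoes alone or in the old AFO, so even the direction is unknown.
- That the shank-angle target of 10-12° gives a yardstick for the bias. It is a target for the tuned combination, not a tolerance for baseline gait, and the protocol states no shoe change to compare with it.

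**Conclusion.** The point holds as a minor defect in a stated sequence. The only baseline gait analysis follows the first intervention step, contrary to its pre-intervention label and to the order used at the T1 visits, and the same-shoe rule comes with no safeguard. Whether this does harm depends on one unstated fact: whether tuning changes the shoe. If it does, two of the three baseline gait conditions are recorded in altered footwear, including the shoes-only reference. If it does not, the footwear concern falls away and only the inconsistent order remains. No bias has been shown, and its size and direction are not derivable. The primary outcomes and the comparison between stiffness configurations are untouched.

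**What to change.** In section 3.5.1, visit III, move the gait analysis ahead of tuning: complete the barefoot, shoes-only and old-AFO trials in unmodified footwear, and then tune the new AFO-footwear combination. Add that any modification made to the footwear during tuning is recorded, so that the state of the shoe is known at every later gait analysis. The tests and the number of visits stay the same, and no extra measurement time is needed beyond noting any footwear change.

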3.5.2 Withdrawal of individual subjects

Subjects can leave the study at any time for any reason if they wish to do so without any consequences. The investigator can decide to withdraw a subject from the study for urgent medical reasons.

3.5.3 Replacement of individual subjects after withdrawal

Withdrawn subjects will not be replaced.

3.5.4 **Premature termination of the study**

The study will only be terminated prematurely for urgent medical or other urgent reasons. In this case only possibly collected data will be analysed.

3.6 Statistical analysis

All statistical analyses will be done with SPSS.

3.6.1 Descriptive statistics

Baseline characteristics of the subjects, such as age, weight, and motor disorders will be summarized using descriptive statistics. Furthermore, for all visits, means, medians, standard deviations, and 95% Confidence Interval (CI) summary statistics on the primary and secondary outcome measures will be presented. In addition, correlations between the parameters will be examined using correlation coefficients and graphical techniques.

3.6.2 Univariate analysis

To analyse differences in AFO efficacy between AFO configurations, means of primary and secondary outcome measures at $T1_{K1}$, $T1_{K2}$, and $T1_{K3}$ will be compared using a repeated measures ANOVA.

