3. METHODS

3.1 Study design

To evaluate AFO efficacy in children with spastic CP, a pre-post experimental study will be performed at the Department of Rehabilitation Medicine of VU University Medical Center (VUmc) in Amsterdam, the Netherlands.

[figure not shown]

Figure 1. Schematic reproduction of the study design. After baseline measurements (T0), the subject's intervention AFO will be prescribed. Stiffness of this AFO will be varied (rigid, stiff and flexible) and the order of AFO stiffness will be block randomized. Accommodation time for each stiffness will last 4-8 weeks, after which effects will be evaluated (T1_{K1}, T1_{K2}, and T1_{K3}). After these evaluations, the subject's optimal AFO will be selected. Follow-up measurements (T2_{Kopt}) will be done after 12-20 weeks. AFO=Ankle-Foot Orthosis; B=Block; K=AFO stiffness; K₁, K₂, and K₃ represent either rigid, stiff or flexible stiffness configuration.

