3.1.1 Data collection and study planning

After enrolling the study (recruitment), baseline measurements (T0) will be performed for the subject, walking with shoes only. Additional measurements will be performed for the subject's current AFO (if applicable). Then, for each subject a new AFO will be prescribed, of which stiffness (K) will be varied into three configurations: rigid, stiff, and flexible (further explained in chapter 5). A balanced block randomization will be applied for six possible sequences of AFO stiffness configurations. Each AFO configuration will be worn for an acclimation period of four to eight weeks, after which AFO efficacy will be evaluated (T1_{k1}

 $,T1_{K2}$ and $T1_{K3}$). An analysis the evaluation of all AFO configurations will lead to selection of the stiffness that results in the most favourable effects for a particular subject, referred to as the subject's optimal AFO. This optimal AFO will be worn for twelve to twenty weeks, after which a second set of follow-up measurements ($T2_{Kopt}$) will be done for the selected optimal AFO (figure 1).

Baseline measurements (T0) will have total duration of 4.5 hour. To limit the burden for the subject, baseline testing will be equally sub-divided into three measurement moments: $T0_{cast}$, $T0_{fit}$, and $T0_{deliver}$ (respectively representing the regular consultancies of casting, fitting and delivery of the new AFO).

The evaluation of AFO efficacy will be done for each configuration, and is referred to as $T1_{k1}$, $T1_{K2}$ and $T1_{K3}$ which represent, dependent on the randomization, either a rigid, stiff or flexible configuration. These measurement moments will last approximately three hours each. Subsequent analysis of these measurements will lead to selection of the subject's optimal AFO. Follow-up measurements for the optimal AFO ($T2_{kopt}$) will be done after wearing the orthosis for twelve to twenty weeks. This broad range of long-term follow-up time is included in the study design, since a child's daily activity and participation will be dependent on environmental factors, such as weather circumstances (e.g. temperature). Measurements at $T2_{kopt}$ will have duration of approximately three hours.

Additional (outside lab) measurements will be performed during baseline (T0_{deliver}), evaluation (T1_{κ}) and follow-up (T2_{kopt}) measurements (table 1).

| Measurement moment | | | Location | Duration |

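### Section 3.6.2 sets out to compare stiffness configurations but names order-of-wear labels, so read literally the repeated measures ANOVA tests period, not stiffness

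*Protocol*

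**What the plan says.** Section 3.6.2 gives its aim and its method in one sentence. The aim: "To analyse differences in AFO efficacy between AFO configurations". The method: "means of primary and secondary outcome measures at $T1_{K1}$, $T1_{K2}$, and $T1_{K3}$ will be compared using a repeated measures ANOVA".

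The labels are defined in other places:

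- Section 3.1.1 says of T1K1, T1K2 and T1K3: "which represent, dependent on the randomization, either a rigid, stiff or flexible configuration". The legends of Figure 1 and of Figure 2 in Appendix A repeat this.
- The Figure 1 legend in section 3.1 adds that "the order of AFO stiffness will be block randomized".
- Section 3.1.1 describes the allocation: "A balanced block randomization will be applied for six possible sequences of AFO stiffness configurations".
- Section 3.5.1 ties the labels to time: "Only during visit IV (T1K1), a 3D-gait analysis with the new configuration (K2) will be performed directly". So K1 is what the child has just worn, and K2 is what comes next.

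Two places use the labels more loosely. Section 3.4.2 gives T1k1 and T1K2 as examples of different configurations, and the note under Table 2 says that T1k is repeated for each of rigid, stiff and flexible. Neither assigns a particular label to a particular stiffness.

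**The concern.** The factor levels named in 3.6.2 do not match the question that the section asks. The question is whether rigid, stiff and flexible differ. The levels named are first, second and third worn. Because order is randomised and balanced, these are close to unrelated: each label holds a mixture of all three stiffnesses.

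The order of the three configurations is the only thing randomised in this study; the rest is pre-post. Section 3.3 describes varying stiffness as what the study primarily investigates. An analyst who followed 3.6.2 to the letter would miss a real stiffness effect and could report habituation, growth or season as a difference between orthoses. Season is a realistic source of drift. Section 3.1.1 itself says that daily activity, one of the two primary outcomes, depends on the weather, and three wear periods of 4 to 8 weeks span 12 to 24 weeks.

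**Working it through.** **Plan's own figure.** Section 3.2.4 uses N = 2·SD²·(Zα + Zβ)²/Δ², with SD 1.70, Δ = 1.26 (25% of 5.02), 80% power and a 0.05 significance level. Read as two-sided: 2 × 1.70² × (1.960 + 0.842)² / 1.26² = 28.58, rounded up to 29. The figure reproduces and is not in dispute here. The 1.26, the 1.70 and the planned 32 children are reused below.

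**Step 1: expected means by label.** Write s_R, s_S and s_F for the three stiffness effects. Among the six sequences, each stiffness stands in each position exactly twice. The stiffness part of the mean at any label is therefore (2s_R + 2s_S + 2s_F)/6, the same for all three labels. If one stiffness lowers energy cost by 1.26, each label shifts by 2 × (−1.26)/6 = −0.42, and the contrast between labels is 0. This needs only balance; no variance or effect size enters.

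**Step 2: expected means under a pure time trend.** Take no stiffness effect and an assumed trend of 0, −0.63, −1.26 over the three periods. By label, the means differ by exactly that trend. By stiffness, each mean shifts by (0 − 0.63 − 1.26)/3 = −0.63, and the contrast is 0. So the comparison by label responds to time and the comparison by stiffness does not.

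**Step 3: rejection rates.** The protocol gives neither a within-child correlation nor a period trend, so both are assumptions. All runs use 32 children allocated in blocks over six sequences, and a test at 0.05.

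| Assumptions | True effect | ANOVA by T1K1/T1K2/T1K3 | ANOVA by rigid/stiff/flexible |
|---|---|---|---|
| SD 1.70, correlation 0.5 / 0.7 | one stiffness −1.26, no trend | about 2% / 1% | about 99% / 100% |
| SD 1.70, correlation 0.5 / 0.7 | no stiffness effect, trend 0/−0.63/−1.26 | about 96% / 100% | about 2% / 1% |
| between-child SD 1.4, within-child SD 0.5 | stiffness 0/−0.4/−0.2, no trend | about 4% | about 79% |
| between-child SD 1.4, within-child SD 0.5 | no stiffness effect, trend 0/−0.3/−0.5 | about 95% | 1–2% |

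Rates below 5% arise because the effect left out of the model moves into the error term.

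**Step 4: sorted by stiffness, with and without a period term.** Without the term, the period spread is added to the within-child variance of 0.5² = 0.25. The addition is roughly the sum of squared deviations of the period effects from their mean, divided by 2. The stiffness effect is 0/−0.4/−0.2 throughout; power figures are simulated and vary by a point or two between runs.

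| Assumed drift | Added variance | Relative to 0.25 | Power without period | Power with period |
|---|---|---|---|---|
| 0/−0.1/−0.2 | (0.01 + 0 + 0.01)/2 = 0.010 | +4% | about 78% | about 80% |
| 0/−0.3/−0.5 | (0.071 + 0.001 + 0.054)/2 = 0.063 | +25% | about 72% | about 81% |
| 0/−0.5/−0.8 | (0.188 + 0.004 + 0.134)/2 = 0.163 | +65% | about 57% | about 81% |

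Under the two larger drifts, type I error without the term is about 1–2%; with it, about 5%.

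**The case against.** The strongest reply is that this is a slip of notation. The sentence opens by stating that configurations are to be compared, the configurations are rigid, stiff and flexible throughout, and both Table 2 and section 3.4.2 speak of T1k as a configuration. A sensible analyst would sort by stiffness, and the damaging rows of the first table would never occur. That stands as a reading of intent. It does not remove the defect. The definitions in 3.1, 3.1.1 and 3.5.1 are explicit, the sentence that fixes the analysis uses the labels so defined, and 3.4.2 repeats the usage.

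Some stronger readings are tempting, and the document does not support them:

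- **That the trial cannot detect a stiffness effect.** The design and the data can; only the comparison as named cannot.
- **That leaving out a period term biases the stiffness test or produces false positives.** Balance keeps the stiffness means essentially free of period effects. Omission makes the test conservative, and the power loss is material only under a drift comparable to or larger than the assumed stiffness effect. The protocol gives no drift. An analysis plan not shown here could also add the term.
- **That children with a missed visit are lost.** This depends on the software procedure, which the protocol does not name, and on missing-data rules that commonly belong in the analysis plan.
- **That a sequence effect is required.** Within-child stiffness contrasts do not need it, and it would use five between-child degrees of freedom.
- **That section 3.6.3 shares the error.** It compares T0, T1K and T2Kopt and does not contrast K1, K2 and K3. The pre-post evaluation of efficacy is therefore untouched.

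**Conclusion.** The point holds as a mismatch between the aim of section 3.6.2 and the factor levels that it names. Read literally, the ANOVA tests period. The zero expected stiffness contrast follows from the balanced six-sequence allocation alone. With 32 children, which is five full blocks of six and two over, balance is near but not exact in any one trial.

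The rejection rates (1–4% by label for a real stiffness effect against 79–100% by stiffness, and 95–100% by label for a pure trend) rest on the assumed variances, correlations and trends and should be read as illustrations. The cause is probably a labelling slip. It still needs correcting before analysis, because it sits in the specification of the only randomised comparison. The period term is a secondary matter of precision: about 72% against 81% power under a drift of 0/−0.3/−0.5, and almost nothing under a small drift.

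**What to change.** 1. In section 3.6.2, make stiffness (rigid, stiff, flexible) the within-child factor and report the contrasts between its levels. State that T1K1, T1K2 and T1K3 denote periods 1 to 3.
2. In section 3.4.2, use stiffness names where configurations are compared.
3. Fit the comparison as a linear mixed model with stiffness and period (1–3) as fixed effects and child as a random effect. Section 3.6.3 already plans mixed models, so no new method or software is involved. That two children fall outside complete blocks of six is a further reason to include period.
4. A sequence effect is optional, and section 3.6.3 needs no change on this ground.

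The cost is a few lines of wording and 2 degrees of freedom: with complete data on 32 children, the residual falls from 2 × 31 = 62 to 60. There is no change to visits, measurements, randomisation or sample size.
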